8.3	Scientific Advisory Board.....	51
8.4	DATA SAFETY MONITORING BOARD (DSMB)	52
9.0	TRIAL MANAGEMENT.....	52
9.1	Statistical Management.....	52
9.2	Data Management.....	52
9.3	STUDY MONITORING.....	53
9.4	PROJECT MANAGEMENT.....	54
10.0	GUIDE TO ACRONYMS / DEFINITIONS	55
11.0	Classes of Anti-Arrhythmic Drugs (Vaughn-Williams Classification)¹²⁷.....	56
12.0	LITERATURE CITED	57

PROTOCOL SYNOPSIS

Title	Vein of Marshall Ethanol Infusion for Persistent Atrial Fibrillation
IND Sponsor	Houston Methodist Research Institute (HMRI) [name]
Name of Product	Dehydrated Alcohol Injection, USP
Clinical Phase	III
Patient Population	Patients with documented, persistent atrial fibrillation (AF that persists beyond 7 days) that have failed to respond to at least one class of antiarrhythmic drugs (due to failure or intolerance), and who are otherwise deemed candidates for radiofrequency ablation of AF.
Objectives	VENUS-AF. Vein of Marshall Ethanol iNfusion in Untreated perSistent Atrial Fibrillation: To assess the role of VOM ethanol infusion in catheter ablation of persistent AF. MARS-AF. Vein of Marshall Alcohol in Repeat ablation of perSistent Atrial Fibrillation: To assess the impact of VOM ethanol infusion after a failed conventional ablation of persistent AF.
Trial Design	Subjects who meet inclusion criteria will be randomized to either a conventional PVAI or PVAI with VOM procedure. Subjects will return for follow-up evaluations at 1, 3, 6, 9, and 12 months. One-month continuous cardiac event monitoring will be performed at 6 months and at 12 months. Studies performed at follow-up visits may include EKG, physical exam, QOL questionnaires, echocardiography, laboratory studies, anticoagulation therapy, and management of adverse events and AF recurrences. Patient and co-investigator performing follow-up of electrocardiographic data will be blinded to the type of procedure. Operator is not blinded.
Sample Size	405 total subjects, VENUS: 180 (VOM-PV) + 156 (PVAI) = 336 MARS: 37 (VOM-PV) + 32 (PVAI) = 69
Primary Endpoints	Efficacy: Freedom from symptomatic AF or atrial tachycardia (AT) AND reduction of AF/AT to less than 30 seconds in a continuous monitor at 6 and 12 months after a single procedure. Safety: Acute procedural complications and total mortality De Novo (VENUS-AF) and Previously Failed Ablation (MARS-AF)

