5.2 STUDY ENDPOINTS

Primary endpoints:

1. Primary Efficacy Endpoint Freedom from AT/AF clinical recurrence on follow-up visits AND less than 30 seconds of AT/AF on a 1 month continuous electrocardiographic monitor at 6 and 12 months.
2. Primary Safety Endpoint - Acute procedural complications and total mortality.

Secondary Endpoints

1. Freedom from AF/AT after >1 procedure.
2. Freedom from AF/AT on antiarrhythmic drugs.
3. AF burden (% time) on continuous monitoring at 6 and 12 months.
4. Procedural parameters: total procedure, fluoroscopy, total RF ablation time (first procedure), and total extent of ablated LA tissue.
5. Clinical/partial success: less than 25% AF burden on a continuous event monitor at 6 and 12 months from ablation procedure.
6. Sub-acute procedural complications (within 30 days).
7. Recurrence as persistent or paroxysmal AF, or flutter after 1 or 2 procedures.

8. LA function on Doppler echocardiography (LA strain^{114ab}) at 12 months.
9. Incidence and mechanisms of atrial flutters.
10. Cardiovascular hospitalizations and
11. QOL as determined by AFEQT questionnaire.

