- e. Documentation of RF time, time to perimitral block (if not already achieved), fluoroscopy time, LA instrumentation time, and procedure time.
- f. Baseline and Final LA voltage map (using any commercially available electroanatomical mapping systems). Measurement of baseline and Final LA scar surface area.

4. Effectiveness (Treatment) Failures

Effectiveness failures towards the primary endpoint will include the following (see Figure 8):

- a. Clinical recurrence of AF or AT after 3-months.
- b. Documented AF or AT of 30 seconds or more on EKG monitor at obtained at 6 and 12 months.
- c. Requirement of a repeat ablation procedure for recurrent AT-AF.
- d. Death.

VENUS and MARS patients who have a recurrence after 3 months post randomization will have a repeat procedure (PVAI). Patients will be deemed to be effectiveness failure for the primary efficacy endpoint of the trial after repeat procedures. Still, subjects will:

- a. Remain in the study for the purpose of all secondary endpoints: these include quality of life, AF burden on event monitoring, success after multiple procedures.
- b. Undergo all clinically necessary procedures and treatments, including prescription of antiarrhythmic therapy and additional procedures needed to control atrial fibrillation or flutter. A crossover VOM procedure will be offered to those randomized to PVAI after 2 in-study procedures.
- c. Data on such additional procedures or treatment will be collected in the Electronic Data Capture system (EDC).
- d. An additional secondary endpoint will be created: total number of procedures performed and requirement of antiarrhythmic drugs.

5. VENUS: Cross-over of patients initially randomized to PVAI only.

If a VENUS patient is originally randomized to conventional PVAI and experiences a treatment failure after a repeat procedure he or she may undergo an additional conventional PVAI ablation procedure during the study. Crossover to VOM ethanol will only be allowed after 2 procedures are performed in the setting of study participation. This is allowed because certain recurrent flutters are particularly suited to respond to VOM ethanol. The primary and secondary endpoints will be computed following their original randomization group.

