6.0 STATISTICAL CONSIDERATIONS

A) Assumptions.

Single-procedure versus multiple-procedure success. Our initial preliminary data suggested an overall procedure success of 45% in patients undergoing PVAI and 61% for those undergoing VOM-PV (difference of 16%). This included patients with repeat procedures performed in some, but not all of the failed procedures (45% all patients in the PVAI group and 30% in the VOM-PV group). **The single-procedure success was 38% in patients undergoing PVAI and 56% in patients undergoing VOM-PV** (difference of 18%). Thus, the endpoint of single-procedure success is likely to show greater differences amongst groups.

Mortality. The expected mortality is low in this study as it has been in AF ablation trials.

Mortality will be recorded as a safety endpoint.

One-year follow-up time. In previous versions of the protocol, additional follow-up time (up to 15 months) was included in the VENUS trial, in order to accommodate for appropriate follow-up of patients undergoing repeat procedures. Therefore, a trial duration of 12 months is sufficient if just single-procedure success is the primary efficacy endpoint. Procedural failures (events counted as the primary efficacy endpoint) occur mostly during the first year. Additionally, 12-month follow-up is consistent with the recommendations for clinical trials in AF by the HRS/EHRA/ECAS Catheter and Surgical Ablation consensus document.²

Unknown classification as success or failure. Patients who cannot be classified as successes or failures on the primary efficacy endpoint will be excluded from the primary analysis.

B) VENUS Group Sequential Clinical Trial Design

Power and sample size determination. Group sequential two proportions power analysis using simulation was performed using PASS V12 (Kaysville, UT). The following assumptions were made:

- Response rate in PV-VOM: $p_1=0.56$
- Response rate in PVAI: $p_2= 0.38$
- Hypotheses: $H_0: p_1= p_2$; $H_1: p_1 \neq p_2$
- Test Statistic: Z-Test (Unpooled)
- Zero Adjustment Method: None
- Alpha-Spending Function: O'Brien-Fleming Analog
- Beta-Spending Function: None
- Futility Boundary Type: None
- Number of Looks: 3
- Simulations: 100000

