1. Freedom from symptomatic AF or flutter AND reduction of AF/flutter to less than 30 seconds in a continuous 4 week monitor at 6 and 12 months	
 12 month continuous ECG page- MARS 12 month continuous ECG page- Venus 	
 6-12 month AF/AT Burden less than 30 seconds on continuous ECG monitoring
2. Safety: Acute procedural complications	
 AE pages Day 7 Telephone FU 	
 Acute AE's related to Day 0 procedure Day 7 reported complications
Secondary Endpoints:		
1. Single vs. 2-procedure success.	
 Status change page 	
 Single: reached primary endpoint #1 after first procedure with no repeats Two procedure: reached primary endpoint #1 after second procedure with no 3rd procedure
2. AF burden (% time) on continuous monitoring at 12 months.	
 6-12 month continuous ECG page- MARS 12 month continuous ECG page- Venus 	
 6- 12 month AF/AT Burden (%) on continuous ECG monitoring
3. Procedural parameters: total procedure, fluoroscopy, total RF ablation time (first procedure), and total extent of ablated LA tissue.	
 PVAI Page VOM page 	
 Total procedure time, PVAI only Total procedure time, VOM procedure Total fluoro time Scar measurements pre and post PVAI and VOM
4. Clinical success: freedom from symptomatic AF/flutter but AF/flutter > 1 min/day < than 1% at 12 months.	
 12 month continuous ECG page- MARS 12 month continuous ECG page- Venus 	
 12 month AF/AT Burden less than 25% continuous event monitor at 6 and 12 months from ablation procedure
5 Sub-acute procedural complications (within 30 days).	
 Symptoms page AE page 	Day 30 reported, procedure related complications via symptoms and/or AEs
6 Recurrence as persistent or paroxysmal AF, or flutter after 1 or 2 procedures.	
 12 lead Ecg page Evaluation for repeat procedure page AE page 	
 Type of recurrence (rhythm) Characterization of recurrence e.g. persistent or paroxysmal for a fib; typical or atypical for a flutter.
7. LA function on Doppler echocardiography (LA strain114ab) at 12 months.	Central echocardiogram page	LA Strain

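### The Section 6.0 C endpoint table words and sources the primary efficacy endpoint differently from Sections 5.2, 5.7, 5.8 and 6.0 A, so some re-ablated patients could be coded as successes

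*Combined protocol and SAP*

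**What the plan says.** **Endpoint table, Section 6.0 C.** The text introduces it as the list of primary outcomes to be analysed at each interim look.

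- Primary endpoint 1, assessed at months 6 and 12, is "Freedom from symptomatic AF or flutter AND reduction of AF/flutter to less than 30 seconds in a continuous 4 week monitor".
- The pages named are the MARS and VENUS 12-month pages, such as "12 month continuous ECG page- Venus". The only data field is "6-12 month AF/AT Burden less than 30 seconds on continuous ECG monitoring".
- Secondary row 1 includes "Two procedure: reached primary endpoint #1 after second procedure with no 3rd procedure".

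**Synopsis.** It also carries the symptom qualifier: "Freedom from symptomatic AF or atrial tachycardia (AT) AND reduction of AF/AT to less than 30 seconds". It adds that this is after a single procedure.

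**Section 5.2.** For months 6 and 12, the endpoint is "Freedom from AT/AF clinical recurrence on follow-up visits AND less than 30 seconds of AT/AF on a 1 month continuous electrocardiographic monitor". There is no symptom qualifier, and clinical recurrence is not defined.

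**Sections 5.7 and 5.8.** Item 3 makes any repeat procedure a failure for the primary efficacy endpoint. Item 4 lists four failures: clinical recurrence after 3 months, 30 seconds or more on the 6- and 12-month monitors, "Requirement of a repeat ablation procedure for recurrent AT-AF", and death.

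**Section 6.0 A.** The VENUS design rests on single-procedure success: "The single-procedure success was 38% in patients undergoing PVAI and 56% in patients undergoing VOM-PV".

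**The concern.** The table feeds the Z-values that are compared with the stopping boundaries, so it has to reproduce the endpoint on which the trial was sized. It departs from that endpoint in three ways.

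1. It asks about symptomatic arrhythmia, where Sections 5.2, 5.7 and 5.8 ask about clinical recurrence.
2. It names no page that carries visit findings, repeat procedures or death. Even its own symptom component therefore has no data source.
3. Its two-procedure row treats primary endpoint 1 as attainable after a repeat, which Sections 5.7 and 5.8 rule out.

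A programmer working from the table and one working from Section 5.7 could classify the same patient differently. Repeats are encouraged within six months of the first procedure, so most would come before the 12-month monitor.

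**Working it through.** **Step 1. Classify the same patients by each rule.**

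| Patient | Failure list, 5.7/5.8 | Wording of the table row | Listed page and field |
|---|---|---|---|
| Re-ablated between months 3 and 6 for a visit-detected recurrence; 6- and 12-month monitors clean | Failure | Failure if the recurrence was symptomatic; the repeat itself is not mentioned | Success |
| Asymptomatic AF on the 9-month visit ECG, no repeat, both monitors clean | Failure only if this is a clinical recurrence (undefined) | Success | Success |
| 30 seconds or more on the 6-month monitor, re-ablated, clean at 12 months | Failure | Failure | Failure by the field's 6-12 month label, though no 6-month page is named |
| Re-ablated, less than one week of monitoring | Failure | Not resolved | Missing, so excluded under 6.0 A |
| Died before study end | Failure | Not mentioned | Failure, by the Missing data paragraph of Section 6.0 |

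Row 1 is a clear conflict between the failure list and the listed source. Row 2 is an ambiguity. Row 4 follows from two rules in Section 6.0: under one week of monitoring is missing, and unclassifiable patients leave the primary analysis. Rows 3 and 5 give no difference in classification.

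**Step 2. Reproduce the plan's power.** Inputs from Section 6.0 B: 180 and 156 patients, rates 0.56 and 0.38, two-sided unpooled Z-test, boundaries 3.953, 2.543 and 2.011 at 60/52, 120/104 and 180/156.

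Final-look approximation: power = Φ(difference / SE − 2.011), with SE = √[p1(1−p1)/180 + p2(1−p2)/156].

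- SE = √(0.2464/180 + 0.2356/156) = 0.05366
- 0.18/0.05366 − 2.011 = 1.344, so power = 0.910

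Simulation of all three looks also gives 0.910. The plan states 0.909, so its figure reproduces.

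**Step 3. Illustrate with the pilot's repeats-included rates.** Section 6.0 A gives 45% and 61%.

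- SE = √(0.2379/180 + 0.2475/156) = 0.05393
- 0.16/0.05393 − 2.011 = 0.956, so power = 0.830; simulation gives 0.83
- Implied change in status: 156 × 0.07 = 10.9 PVAI patients and 180 × 0.05 = 9.0 VOM-PV patients

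**Step 4. Assumed range.** The documents give no success rate under the table's coding. Suppose a share of the expected failures (156 × 0.62 = 96.7 PVAI, 180 × 0.44 = 79.2 VOM-PV) is recoded as success.

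| Share recoded, PVAI / VOM-PV | Difference (points) | Simulated power |
|---|---|---|
| 5% / 5% | 17.1 | 0.88 |
| 10% / 10% | 16.2 | 0.84 |
| 20% / 20% | 14.4 | 0.76 |
| 30% / 30% | 12.6 | 0.66 |
| 20% / 10% | 10.0 | 0.45 |

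The pilot's shift corresponds to nearly equal shares: 0.07/0.62 = 11.3% and 0.05/0.44 = 11.4%. The unequal last row is an assumption with no support in the documents.

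**The case against.** The strongest reply is that the table is an index of storage locations and was never meant to replace the failure list. Sections 5.7 and 5.8 state the repeat rule plainly, the synopsis says single procedure, and the status-change page, listed for a secondary endpoint, records repeats. A careful analyst would probably apply Section 5.7. That limits the harm but does not remove the conflict. The table is presented as what is analysed at the interim looks, and its two-procedure row contradicts the repeat rule outright.

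Several stronger readings are tempting, and the documents do not support them:

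- **That deaths would be counted differently.** The Missing data paragraph already treats death as non-response. Only the source page is unlisted.
- **That AF on the 3-month ECG separates the definitions.** That visit sits at the edge of the blanking period described in Sections 4.3 and 5.6. AF within blanking counts under neither definition.
- **That a patient re-ablated after a positive 6-month monitor passes.** The row's text and its field label both include month 6. Two of the three repeat indications in Section 5.7 are findings on that monitor.
- **That the synopsis also admits repeats.** It does not. It differs from Section 5.2 only on symptoms.
- **That the symptom wording is a proven contradiction.** Clinical recurrence is undefined, and the plan may use the two terms interchangeably: for clinical success, Section 5.7 uses one and the table the other.
- **That the trial loses 8 points of power.** The 45% and 61% come from a pilot in which only some failures were re-ablated, and Section 4.2 calls the same 45% a single-procedure rate. They do not estimate the table's coding, which still asks for a clean 6-month monitor.

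**Conclusion.** The inconsistency is real and concerns the primary efficacy endpoint of both VENUS and MARS. The firm part is narrow: the listed field would pass patients re-ablated between months 3 and 6 for a visit-detected recurrence whose monitors are clean, and secondary row 1 treats such a result as reaching primary endpoint 1. The asymptomatic 9-month ECG case is unresolved rather than contradictory.

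The number of patients affected cannot be derived from the documents. The fall from 0.91 to about 0.83 is an illustration that assumes the pilot's repeats-included rates stand in for the table's coding. The plan's sample size and stated power are correct for the single-procedure endpoint. The point should be settled before any primary outcome is coded for an interim look, because the classification of a repeat should not depend on which section the programmer reads.

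**What to change.** 1. Make the four-item failure list of Sections 5.7 and 5.8 the single primary definition, and refer to it in the synopsis, Section 5.2 and the table.
2. Define clinical recurrence. State whether asymptomatic AF or AT on a post-blanking visit ECG is one, and align or remove the word symptomatic accordingly.
3. In the table, list as sources the 6- and 12-month monitor pages and the visit-ECG, repeat-procedure/status-change and death pages.
4. Derive success as none of the four failures. A documented repeat or recurrence is then a failure even when monitor data are missing.
5. Reword secondary row 1 so that two-procedure success has its own definition and is not described as reaching primary endpoint 1.

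The cost is wording plus one derivation rule. Sample size, stated power and data collection do not change.

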- 2. Thirty-day (30D) follow-up (+/- 10 days).** Follow up evaluation will include an EKG, assessment for complications including a targeted physical exam and a review of adverse events and concomitant medications (limited to AAD and anticoagulants) will be documented. Routine medications, including AAD may be continued. Symptomatic AF or flutter should be treated with AAD or cardioversion as needed but will not be recorded for endpoint assessment.
- 3. Three-month (90D) follow-up (+/- 30 days).** Evaluation will include an EKG, and assessment for complications, targeted physical exam and a review of adverse events and concomitant medications (limited to AAD and anticoagulants) will be documented. If the patient is in AF or flutter, a cardioversion will be performed electively within 2 weeks so that all patients are in sinus rhythm after the 3 month blanking period. AAD therapy will be discontinued in all patients at this time if they are clinically stable and in sinus rhythm.
- 4. Six-month (180D) follow-up up (+/- 60 days).** Follow up evaluation will include an EKG, and physical exam. Additionally, patients will fill out the AFEQT¹¹³ QOL questionnaire and will undergo a 3-4 week continuous EKG monitor (4 weeks if tolerated by patient) (see *Core laboratories*, below). Subjects who have a miniaturized, implantable rhythm recording device (such as Medtronic LinQ and others) or an implanted pacemaker/defibrillator may have the continuous rhythm data obtained from that device, and may forego the portable recorder. The purpose of this EKG monitor (4 weeks if tolerated by patient) is to screen for recurrent AF that may prompt an early repeat procedure. Patients that have clinical or EKG recurrences will undergo a PVAI procedure (see below and Figure 8).
- 5. Nine-month follow-up up (+/- 30 days).** Follow up evaluation will include an EKG and physical exam. Patients that have clinical or EKG recurrences will undergo a repeat PVAI procedure. The timing of a repeat procedure will be encouraged to be within 6 months of randomization.
- 6. Twelve-month follow-up up (+/- 60 days).** Follow up evaluation will include an EKG, and physical exam. Additionally, patients will fill out the AFEQT¹¹³ QOL questionnaire

and undergo a continuous EKG monitor (4 weeks if tolerated by patient) to determine the primary efficacy endpoint.

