5.7 VENUS: DEFINITIONS OF PROCEDURAL SUCCESS OR FAILURE AND INDICATIONS FOR REPEAT PROCEDURES

- 1. Success:** Freedom from AT/AF clinical recurrence on follow-up visits AND less than 30 seconds of AT/AF on a 1 month continuous electrocardiographic monitor .
- 2. Clinical Success.** Freedom from AT/AF clinical recurrence on follow-up visits but documented AF or flutter up to 25% of the time on a 1-month continuous electrocardiographic monitor. The rationale is to account for patients in whom a repeat procedure would not be clinically indicated, yet AF/AT would not be considered cured.
- 3. Repeat procedures. A repeat procedure will constitute an effectiveness failure for the purpose of the primary efficacy endpoint.** However, repeat procedures and their outcomes will be recorded for secondary outcome analysis. First, repeat procedures are a clinical reality in persistent AF, and a single-procedure success endpoint –does not capture it. Second, it is possible that VOM-PV on a first procedure may increase success of a second procedure –e. g. if the recurrences in VOM-PV group are as AT instead of AF. Both represent a clinical failure of the procedure, but a repeat procedure for AT is more likely to succeed.⁶⁵ Repeat procedures will be encouraged to be timed within the first 6 months of the randomization procedure. Although this may seem short, it is our clinical experience that the bulk of AF recurrences tend to occur shortly after the blanking period.¹¹⁵ Thus, we expect a minority of patients to recur late in this window.

Indications for a repeat procedure include:

- Procedure failure: Symptomatic, recurrent persistent AF or flutter detected clinically during the scheduled follow-up visits.
- Less than partial/clinical success: AF or flutter burden on electrocardiographic monitoring exceeding 25% regardless of symptoms. Monitoring will be performed at 6 months post randomization procedure.
- Symptomatic AF or flutter detected on electrocardiographic monitoring regardless of AF or flutter burden. Monitoring will be performed at 6 months post randomization procedure.

Data to be collected during a repeat procedure will include

- a. Documentation of PV isolation: number and location of reconnected PV at the baseline of the repeat procedure.
- b. Perimitral conduction: presence or absence of perimitral block.
- c. Mechanisms of atrial flutter, if present.
- d. Documentation of other RF ablation sites

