Missing data. The critical piece of data required for endpoint analysis is the electrocardiographic event monitor. Failure to comply with wearing the monitor will lead to missing data. We request patients to wear monitors for 1–month. However, only a minimum of 1-week of monitored time is required for Endpoint assessment. Patients with less than 1 –week of monitoring will be considered as missing data. Patients who die before then study end will be considered not to have a response to treatment. For patients with missing primary outcomes, we will perform multiple imputation (MI) based on Monte Carlo Markov chain (MCMC) methods (Refs 1-3). MI will only be used for dealing with missing data as a secondary analysis tool of the primary endpoint. In Stata, MI is available for many procedures, especially the regression modules (linear, logistic, Poisson, Cox PH). MI can be performed to iteratively impute central estimates of missing outcome measures based on subjects' covariate patterns. The most straightforward example can be envisioned in this study, where logistic regression with MI is employed to train a model based on primary outcome (0-failure,1-success) as the dependent variable and age, gender, baseline AF duration, and baseline LA volume as independent predictors to impute $P(y=1|x)$ for subjects with missing primary outcome.

Sensitivity analysis. Following methods introduced in Proschan et al. (Ref 4), we simulated success rates for patients with missing 12-month outcomes in VOM and PVAI arms for VENUS and MARS at 33%, 66%, and 100% information time (looks 1-3). $B=100,000$ iterations were used with proportions of $P_m=0, 0.05, 0.10, 0.15$, and 0.2 representing the amount of missing data in both VOM and PVAI arms. At look k , let the success rate in the VOM arm be p_{1k} and the success rate in the PVAI arm be p_{2k} , n_{1k} and n_{2k} the number of patients accrued in the VOM and PVAI arms, $n_{1k}^m = n_{1k}P_m$ and $n_{2k}^m = n_{2k}P_m$ the number of patients in VOM and PVAI arms with missing outcome data, and $n_{1k}^0 = n_{1k} - n_{1k}^m$ and $n_{2k}^0 = n_{2k} - n_{2k}^m$ the number of patients in VOM and PVAI arms without missing outcomes. Next, for VOM patients with missing

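### The Section 6.0 analysis table caps clinical success at 1% burden where every other definition uses 25%, and the 25% definitions also differ among themselves

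*Combined protocol and SAP*

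**What the plan says.** Clinical success is defined in several places in the combined protocol and SAP.

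- **Section 6.0, Statistical Analyses, endpoint table, secondary endpoint 4, endpoint column:** "freedom from symptomatic AF/flutter but AF/flutter > 1 min/day < than 1% at 12 months".
- **Same row, data-field column:** "12 month AF/AT Burden less than 25% continuous event monitor at 6 and 12 months from ablation procedure". The column naming the data-capture pages lists only 12-month pages for this row.
- **Section 5.2, secondary endpoint 5, and the synopsis:** "Clinical/partial success: less than 25% AF burden on a continuous event monitor at 6 and 12 months from ablation procedure". Neither states a symptom or recurrence condition.
- **Sections 5.7 (VENUS) and 5.8 (MARS), item 2:** the patient has no clinical recurrence at follow-up visits but has "documented AF or flutter up to 25% of the time on a 1-month continuous electrocardiographic monitor". The rationale given is to describe patients who would not need another procedure and yet would not be regarded as cured. Item 2 names no time point.
- **Sections 5.7 and 5.8, indications for a repeat procedure:** "Less than partial/clinical success: AF or flutter burden on electrocardiographic monitoring exceeding 25% regardless of symptoms".

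On recording length, Section 5.6 asks for three to four weeks at six months and four weeks, if tolerated, at twelve months. The missing-data text in Section 6.0 says that "only a minimum of 1-week of monitored time is required for Endpoint assessment".

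The text introducing the table says that its secondary outcomes are analysed and reported before each DSMB review meeting. Nothing says which definition governs if they differ.

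**The concern.** The table is the part of the plan that a programmer would work from. Its endpoint column and data-field column give different thresholds for the same outcome in the same row, and both cells are legible current text. If the endpoint column is programmed, patients whom the rest of the protocol counts as clinical successes are counted as failures.

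Replacing 1% by 25% would not finish the job. The 25% statements leave open whether a patient with no recorded arrhythmia at all is a clinical success, whether a clinical recurrence disqualifies, and whether the rule applies at 12 months or at 6 and 12 months. If these choices are made after unblinded data are seen, the arm rates, and possibly the direction of the comparison, depend on the choice.

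**Working it through.** The plan assigns no power, alpha or expected rate to this endpoint, so there is no stated figure to reproduce. The check sets the definitions side by side and then sizes the differences.

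**1. Definitions compared**

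- Upper limit: under 1% (endpoint cell); under 25% (data field, 5.2, synopsis); at most 25% (5.7, 5.8).
- Lower limit: more than 1 min/day (endpoint cell); none stated (data field, 5.2, synopsis); some documented arrhythmia (5.7, 5.8).
- Symptom or recurrence condition: no symptomatic arrhythmia (endpoint cell); no clinical recurrence at visits (5.7, 5.8); none (data field, 5.2, synopsis).
- Timing: 12 months (endpoint cell); both 12 months and 6 and 12 months (data field); 6 and 12 months (5.2, synopsis); unstated (5.7, 5.8, item 2).

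**2. The upper limits in hours**

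Ratio of limits: 25% / 1% = 25. Per day, 1% of 1,440 min = 14.4 min and 25% = 360 min. Over a recording of d days, hours = proportion × d × 24:

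- 7 days (168 h): 1.68 h against 42 h
- 21 days (504 h): 5.04 h against 126 h
- 28 days (672 h): 6.72 h against 168 h

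Consider a patient with neither symptomatic arrhythmia nor clinical recurrence whose burden is from 1% to under 25% at each assessment. That patient is a clinical success under the data field, the synopsis, 5.2, 5.7 and 5.8, and is not one under the endpoint cell.

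**3. The lower limit**

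1 min/day is 1/1,440 = 0.069% burden. Read as an average, it is 28 min over 28 days. A symptom-free patient with a 30-second episode and no more than 28 min in total then fails the primary endpoint and is also not a clinical success under the cell. A symptom-free patient with 6 h (6/672 = 0.9%) is a clinical success under it.

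**4. Including or excluding full successes**

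Inputs: planned VENUS single-procedure success of 0.56 (VOM-PV) and 0.38 (PVAI), from Section 6.0. Assumptions, for illustration only: the same fraction f of the remaining patients in each arm meets the partial criterion, and the denominator is everyone analysed in the arm. The documents do not give f.

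- Included: (0.56 + 0.44f) − (0.38 + 0.62f) = 0.18(1 − f)
- Excluded: 0.44f − 0.62f = −0.18f

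At f = 0.1 the differences are +0.162 and −0.018. At f = 0.5 they are +0.09 and −0.09. Under these assumptions the sign differs for every f strictly between 0 and 1.

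**The case against.** The strongest reply is that the intended threshold is not in real doubt. The 25% figure stands in the synopsis, 5.2, 5.7, 5.8 and the data field, and the repeat-procedure text in 5.7 and 5.8 places burden above 25% outside clinical success. A reader might infer from the table that the threshold is an open choice across a 25-fold range. The documents do not support that: one cell contradicts five other places. The error in the cell still stands, because the cell is in the operative table.

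A second reply is that 5.2 is a one-line list and that 5.7 and 5.8 supply its operational detail. That is a fair reading, and their rationale does point to a category separate from full success. That 5.2 includes full successes follows only from its literal wording; the protocol does not say it was intended. This part is therefore a request to reconcile and is weaker than the 1% against 25% contradiction.

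A third reply is that little is lost. AF burden as a percentage is a secondary endpoint in its own right, so either threshold can be computed later from the same data. This is correct. It limits the harm but does not settle which result is the planned one.

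**Conclusion.** The contradiction in the table is real, and the documents point clearly to 25%. The 1% and 1 min/day limits are probably leftover wording; that is an inference. The reclassified group is patients without symptomatic arrhythmia or clinical recurrence whose burden is from 1% to under 25%: 1.7 to 42 hours on the shortest accepted recording, 6.7 to 168 hours on 28 days.

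Two stronger statements might be inferred and are not supported. The first is that every patient between the two limits changes category. A patient with a symptomatic clinical recurrence fails under the endpoint cell and under 5.7/5.8 alike, and changes only against a rule based on burden alone. The second is that the handling of full successes matters more than the threshold. No distribution of burden is given, so the two effects cannot be ranked. What can be said is that, under the equal-fraction assumption, handling of full successes moves the expected VENUS difference from +0.18(1−f) to −0.18f.

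This is one of several secondary endpoints. The primary endpoint (30-second criterion), the sample size and the stopping boundaries do not use it. It should be corrected, but it does not threaten the main conclusion of the trial.

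**What to change.** In the Section 6.0 table, replace the 1% and 1 min/day wording for secondary endpoint 4 with the 25% burden threshold used in the other five places. Copying the data field unchanged would not be enough, because it gives two timings and no recurrence condition.

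Then state one definition, in identical terms, in the synopsis, 5.2, 5.7, 5.8 and both columns of the table row. It should settle:

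- the time point or points, and whether the criterion must be met at each;
- whether freedom from symptomatic arrhythmia or from clinical recurrence is required;
- whether full successes count as clinical successes, and the denominator;
- how a burden of exactly 25% is classified.

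If the sponsor did intend a different limit in the table, the reason should be given there. The definition should be fixed before any unblinded analysis of this endpoint. The cost is wording only: no new data are needed and no repeat-procedure rule needs to change.
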